4.4.12 Hemophilia Joint Health Score

Hemophilia Joint Health Score (HJHS) is a functional measure of joint health using ankle, knee and elbow (to access flexion, extension, range of movement, muscle strength, swelling, duration of swelling, crepitus, gait, pain, and muscle atrophy). The assessment is administered by a healthcare professional trained in the use of anthropometric measures. Ideally HJHS should be performed and assessed by the same investigator or designee at each time point. The HJHS will be used in children aged \geq 4 years at Baseline, Week 26 and Week 52. Details of the questionnaire are provided in protocol Appendix 6 (Section 10.7.3).

Range	Left elbow	Right elbow	Left knee	Right knee	Left ankle	Right ankle	Domain total
Swelling	0-3	0-3	0-3	0-3	0-3	0-3	0-18
Duration	0-1	0-1	0-1	0-1	0-1	0-1	0-6
Muscle Atrophy	0-2	0-2	0-2	0-2	0-2	0-2	0-12
Crepitus on motion	0-2	0-2	0-2	0-2	0-2	0-2	0-12
Flexion loss	0-3	0-3	0-3	0-3	0-3	0-3	0-18
Extension loss	0-3	0-3	0-3	0-3	0-3	0-3	0-18
Joint pain	0-2	0-2	0-2	0-2	0-2	0-2	0-12
Strength	0-4	0-4	0-4	0-4	0-4	0-4	0-24
Joint Total	0-20	0-20	0-20	0-20	0-20	0-20	

Table 4 - HJHS domains

The HJHS assessment includes the scoring of six joints (left ankle, right ankle, left elbow, right elbow, left knee, and right knee) on a scale from 0 to 20 according to the following criteria: swelling, duration of swelling, muscle atrophy, crepitus of motion, flexion loss, extension loss, joint pain, and strength (Table 4). Gait will be scored on a scale from 0 to 4 based on the number of skills that are not within the normal limits. The total score will be the sum of scores from all six joints plus the gait score (range from 0 to 124, with 0 being normal and 124 being the most severe disease).

The total joint score (ie, sum of scores from all six joints) will be defined and derived as follows:

- The total joint score will be set as missing if any one of the individual item score at any joint is missing;
- The total joint score will be set as missing if scores are evaluated within 2 weeks after a joint or muscle bleeding episode; and
- The total joint score will be re-derived if surgery is performed on a joint. The scores for that joint will be replaced with the scores of the same joint at the last visit prior to the surgery using the last observation carried forward (LOCF) technique. Then, the total joint score in the subsequent visits are re-derived using the abovementioned scores.

The individual domain score (ie, sum of scores from all six joints for each domain) will be calculated using the same rules as above for all domains.

The total joint score, gait scores, and total score (calculated as the sum of total joint score and gait score), as well as change from baseline will be summarized by age cohort and overall. In addition, individual domain scores and change from baseline will be summarized by age cohort and overall.

4.4.13 Haemo-QoL (≥4 years old)

Four HAEMO-QoL questionnaires are used in this study and administered at Baseline, Weeks 26 and 52. Details of the questionnaires are provided in protocol Appendix 6 (Section 10.7.5.2).

- Haemo-QoL kids short version (4-7 years)
- Haemo-QoL kids short version (8 to <12 years)
- Haemo-QoL parent proxy short version (for participants 4-7 years)
- Haemo-QoL parent proxy short version (for participants 8 to <12 years)

Each HAEMO-QoL questionnaire for 4-7 years will be summarized by calculating a total score, and each questionnaire for 8 to <12 years will be summarized in terms of subscale scores and a total score according to the recommendations of the questionnaire authors. As specified in Appendix 5.2 Haemo-Qol (Section 5.5.2), questions will either have been coded or will be recoded to ensure that high scores represent a low quality of life and low scores represent a high quality of life. These scores are then transformed to produce a Transformed Scale Score (TSS). This score is scaled, as a percentage, from 0 to 100%, with higher TSS values representing a worse quality of life for each sub-score and total score summary measurement.

When missing data are presented, a subscale/total score can only be calculated if at least 50% of questions for that subscale/questionnaire are answered (non-missing and not "Not Applicable").

For each HAEMO-QoL questionnaire, the total score and individual subscale scores based on the TSS will be summarized descriptively for the actual value and change from baseline by visit for each age cohort and overall.

4.4.14 Surgery endpoints

An overall summary of surgeries will be provided which summarizes the number of major and minor surgeries and (%) of participants with at least one major surgery and (%) of participants with at least one minor surgery.

All major and minor surgeries in detail will be provided in the data listings.

4.4.14.1 Investigators' or Surgeons' assessment of participant's hemostatic response to BIVV001 treatment

The Investigators'/Surgeons' assessment of the participant's hemostatic response to BIVV001 treatment will be collected at 24 hours post-surgery based on the ISTH 4-point response scale and will be summarized categorically and using descriptive statistics for all major surgeries for participants in the surgery subgroup. Categorically, the number and percentage of surgeries given each rating will be tabulated. Percentages will be based on the number of surgeries for which a response was provided. Since the response is given as an ordered ordinal scale, the responses have also been given a numeric score (Excellent=1, Good=2, Fair=3, Poor/none=4). A lower average score indicates a better Investigators'/Surgeons' assessment of the participants' response to surgery with BIVV001 treatment. Descriptive statistics will be provided using the numeric value of the 4-point scale.

4.4.14.2 Number of injections and dose to maintain hemostasis for major surgery

The number of injections, mean dose per injection (IU/kg), and total dose (IU/kg) required to maintain hemostasis during surgery will be summarized for all major surgeries for participants in the surgery subgroup. The number of injections per surgery will be summarized categorically (0, 1, 2, 3, 4, >4) and with descriptive statistics. Percentages for the categorical summary will be based on the number of major surgeries. The mean dose per injection and total dose required to maintain hemostasis will be summarized using descriptive statistics. The mean dose per injection will be determined as the average dose across all injections per major surgery (including the loading dose); the total dose will be determined as the sum across all injections (including the loading dose) per major surgery.

4.4.14.3 Total BIVV001 consumption for major surgery

Total consumption (IU/kg) per major surgery on the day of surgery, for the first 2 weeks following surgery (Days 1-3, 4-14, and 1-14), and for the overall surgical/rehabilitation period will be summarized using descriptive statistics for all major surgeries for the surgery subgroup. The day of surgery refers to the calendar day of the surgery and includes the loading dose given for that surgery. The first 2 weeks following surgery begins the day after surgery and extends for 14 calendar days. The overall surgical/rehabilitation period is defined in Section 4.1.1.3. Total BIVV001 consumption will be determined as the sum of all doses administered during the referenced time periods.

4.4.14.4 Number and type of blood component transfusions for major surgery

The number of transfusions per surgery (regardless of the type of transfusion), the number of transfusions summed across all surgeries for each type of transfusion, and the number of surgeries requiring each type of transfusion will be summarized categorically for all major surgeries for the surgery subgroup. Percentages in the categorical summaries will be based on the number of major surgeries for which the respective data is available.

4.4.14.5 Estimated blood loss for major surgery

The estimated total blood loss during and post each major surgical procedure will be summarized using descriptive statistics for all major surgeries for the surgery subgroup.

4.5 EXPLORATORY ENDPOINTS ANALYSES

4.5.1 **PROMIS** instruments

Six PROMIS instruments are used in this study and administered at Baseline, Weeks 26 and 52. Details for each instrument are provided in protocol Appendix 6 (Section 10.7.5.1).

- PROMIS Pediatric NRS Pain Intensity (v1.0 Pain Intensity $1a; \geq 8$ years old)
- PROMIS Pediatric-SF Pain Interference (v2.0 Pain Interference $8a; \ge 8$ years old)
- PROMIS Pediatric-SF Physical Activity (v1.0 Physical Activity 8a; \geq 8 years old)

- PROMIS Parent Proxy NRS Pain Intensity (v1.0 Pain Intensity 1a; 5 to <12 years old)
- PROMIS Parent Proxy-SF Pain Interference (v2.0 Pain Interference 8a; 5 to <12 years old)
- PROMIS Parent Proxy-SF Physical Activity (v1.0 Physical Activity 8a; 5 to <12 years old)

The two PROMIS instruments on pain intensity each uses an 11-point Numeric Rating Scale (NRS) ranging in value from 0 to 10, with 0 indicating no pain and 10 indicating worse pain. The NRS will be summarized descriptively for the actual value and change from baseline by visit for each age cohort and overall.

For each of the other four PROMIS instruments, each question has five response options ranging in value from one to five. To find the total raw score for an instrument with all questions answered, sum the values of the response to each question. All questions must be answered in order to produce a valid total score. The total raw score is then converted into a T-score for each participant using an instrument-specific *Conversion Table* (see APPENDIX 5.1 PROMIS instruments [Section 5.5.1]). The T-score rescales the raw score into a standardized score with a mean of 50 and a standard deviation (SD) of 10. Therefore, a person with a T-score of 40 is one SD below the mean.

A higher PROMIS T-score represents more of the concept being measured. For negativelyworded concepts like Pain Intensity and Pain Interference, a T-score of 60 is one SD worse than average. By contrast, for positively-worded concepts like Physical Function and Physical Activity, a T-score of 60 is one SD better than average.

T-scores for each of the four PROMIS instruments will be summarized descriptively for the actual value and change from baseline by visit for each age cohort and overall.

4.5.2 EuroQoL-Youth (EQ-5D-Y)

The EuroQol-5D-Youth (EQ-5D-Y) and its parent proxy version will be used for children aged 8 to <12 years and children aged 4-7 years, respectively, at Baseline, Weeks 26 and 52. Both instruments consist of 3 pages: the title page, the EQ-5D-Y descriptive system and the EQ visual analogue scale (VAS). A copy of the questionnaires is provided in protocol Appendix 6 (Section 10.7.5.3).

Both the EQ-5D-Y children and parent proxy versions will be analyzed according to the recommendations of the authors (see www.euroqol.org). The descriptive system contains 5 dimensions (mobility, looking after myself, doing usual activities, having pain or discomfort, feeling worried, sad or unhappy), each with 3 response categories (no problems, some problems, and a lot of problems). The number and percentage of participants in each response category will be tabulated by age cohort and overall. Percentages are based on the number of participants for whom an assessment is provided at the respective visit.

The EQ visual analogue scale is a visual scale from 0-100 to record a respondent's overall selfrated health state. The respondent is asked to mark an "X" on the scale then record the corresponding number; 0 refers to the worst possible health state, 100 refers to the best possible health state. The EQ VAS will be summarized for the observed response and change from baseline by visit for each age cohort and overall.

4.5.3 Caregiver interviews

The caregiver interviews data is not the scope of this SAP and will be analyzed in a separate report.

4.5.4 Healthcare resource utilization (HRU)

The number (0, 1-2, 3-4, >4) and percentage of healthcare visits by type (office visit, hospital ER visit, hospitalization, and ICU stay) will be summarized by-visit and age cohort and overall for the FAS.

4.6 MULTIPLICITY ISSUES

All analyses are descriptive in nature and therefore adjustments for multiplicity will not be applied.

4.7 SAFETY ANALYSES

The summary of safety results will be presented by age cohort as well as overall for the Safety Analysis Set. The analysis of the safety variables will be essentially descriptive, and no systematic testing is planned.

4.7.1 Extent of exposure

The extent of exposure and compliance will be assessed and summarized by age cohort and overall. In addition, study drug administered will be listed by participant including the reason for administration, date and time of administration, and dose. A listing of lot numbers and nominal potency of the lots will be provided by participant.

Except for PK doses, the unit body weight dose (IU/kg) for analysis of dosing will be calculated as the total IU (nominal dose) for each injection divided by the participant's most recent weight in kg prior to the dose of study drug.

PK doses are calculated using the actual potency of the vial (between 80% to 125% of nominal strength) and used partial vials where necessary. Therefore, PK doses in the analysis are similarly calculated using the exact number of complete and partial vials, the volume and actual potency of each vial and the participant's most recent weight:

$$Dose (IU/kg) = \frac{\left(\frac{\text{Total volume administered}}{\text{Volume of vial}}\right) \times \text{Actual Potency of Vial}}{Weight (kg)}$$

Weight (kg)

4.7.1.1 Overall exposure

The extent of investigational medicinal product (IMP) exposure will be assessed by the number of injections and exposure days to BIVV001 and duration of BIVV001 dosing based on the Safety Analysis Set.

Number of Injections and Exposure Days to BIVV001

For any participant, the total number of days of exposure to BIVV001 will be accumulated from the time of their first on-study injection of BIVV001. An ED is a 24-hour period in which one or more BIVV001 injections are given. The 24-hour window starts from the first injection on study and then for subsequent injections, it starts from an injection taken after/outside of a previously identified ED.

The total number of EDs on BIVV001 for each participant will be summarized categorically (<5, 5-<10, 10-<25, 25-<50 and \geq 50; and \geq 1, \geq 5, \geq 10, \geq 25, \geq 50) and with descriptive statistics for the Safety Analysis Set.

The total number of injections per participant will be summarized overall and by reason for injection (prophylactic regimen, spontaneous bleed, traumatic bleed, follow-up injection, surgical or other) using descriptive statistics for the Safety Analysis Set.

Duration of BIVV001 Dosing

The duration of BIVV001 dosing will be calculated from the start date time of the treatment dose to the end date time, as defined in Section 4.1.1.1. Any interruptions to dosing will not be accounted for when calculating this duration.

Duration of BIVV001 dosing (weeks) will be summarized using descriptive statistics for the Safety Analysis Set. Weeks will be represented in the descriptive statistics as if these were data collected with 1 decimal place. The number and percentage of participants whose duration of dosing was at least 13, 26, 39, and 52 weeks will be summarized.

4.7.1.2 Compliance

Compliance will be assessed during the efficacy period and will be summarized for the FAS by age cohort and overall. Except for doses administered in the clinic, study treatment may be administered by the participant or a caregiver. Data from the eCRF and ePD will be considered for the analysis of treatment received and participants' compliance with the study protocol.

Compliance of prophylaxis injections

The compliance rate of each participant during the efficacy period will be calculated in 2 ways: As dose compliance and as dosing interval compliance. Compliance will first be determined on a per-injection basis and then on a per-participant basis. That is, compliance for an individual dose or dosing interval will be determined and then the overall percentage of doses and dosing intervals that were in compliance will be determined for each participant. For the purpose of evaluating compliance, the following will be considered per injection:

- The nominal dose taken compared to the study dose (50 IU/kg for prophylaxis treatment)
- The actual day of treatment compared to the study day of treatment (weekly for prophylaxis treatment)

An individual dose will be considered compliant if it is within 80%-125% of the study dose (50 IU/kg). An individual dosing interval will be considered compliant if the time between two prophylactic doses is within 36 hours of the study dosing interval (7 days).

The actual dosing intervals will be calculated as the length of time between consecutive prophylactic doses that are not separated by a bleeding episode or surgical/rehabilitation period (date / time of dose_{x+1} – date / time of dose_x). The actual time between doses will be determined in minutes and converted to days as the number of minutes divided by 1440. The absolute value of the difference between the actual dosing interval and the study dosing interval of 7 days must be ≤ 1.5 day (+/-36 hours) in order to be compliant.

All prophylactic injections will be used to determine prophylactic dose compliance; only the prophylactic dosing intervals that are not separated by a bleeding episode or surgical/rehabilitation period will be used to evaluate prophylactic interval compliance. Large injection intervals as defined in Section 4.1.1.2 will be included in the interval compliance calculation. Dose and dosing interval compliance rates per participant will be determined as follows:

where the percentage of a study dose is calculated as: (nominal dose taken / study dose) \times 100.

Dose interval compliance rate =
$$\frac{\text{Number of doses taken within +/-36 hours of}}{\text{Study day/time}} \times 100$$

Both participant dose and dosing interval compliance rates will be summarized as continuous variables using descriptive statistics as well as categorically (<80%, $\ge80\%$) for the FAS.

A participant is considered "dose compliant" or "dosing interval compliant" if his respective rate is at least 80%. Based on this, participants will be further classified into the following mutually exclusive categories for overall compliance to their prophylactic treatment as:

- Both dose and interval compliant
- Dose compliant or interval compliant (but not both)
- Neither dose nor interval compliant

Compliance of ePD contemporaneous data entry

Injections (for prophylaxis or a bleed) and untreated bleeds must be entered into the ePD within 7 days from the date of the injection or the untreated bleed. Injections or untreated bleeds entered outside the 7-day window will be reported as protocol deviations. Descriptive statistics of the percentage of the participants with fewer than 80% of their total individual ePD records entered within this 7-day window and those with \geq 80% of records meeting this criterion will be presented for the FAS as well as a summary of % compliance to this criterion by participant.

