6.1.6.2 Calculation and recording of actual versus nominal dosing

Actual potency must be used for dose calculations for the following:

Baseline PK and Peak/Trough at Week 4: Dose for PK is 50 IU/kg. The **actual** potency shown on the vial must be used to calculate the volume of BIVV001, using partial vial(s). The instructions provided in the Pharmacy Manual must be used to calculate the *volume for administration based on actual potency*.

Nominal strength can be used for dose calculations for the following:

Peak/Trough after Week 4 and dosing for prophylactic treatment or treatment of bleeds. The **nominal** strength should be used for calculations and rounded up to the nearest whole vial. Note: The instructions provided in the Pharmacy Manual must be used to calculate the *number of vials for administration based on nominal strength* (unless an equivalent alternative site-specific template is approved by the clinical research associate [CRA] prior to use).

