4.1.1.2 Efficacy period

The efficacy period will be used for the evaluation of bleeding and consumption endpoints. For a participant to have an evaluable efficacy period over the duration of study, he/she must have at least 2 prophylactic dose of study drugs. The efficacy period is defined as the treatment period interrupted for PK periods, surgical/rehabilitation periods (major and minor) and large injection intervals as described below.

Adjustments Due to PK sampling period(s)

For participants undergoing PK sampling after their first dose of BIVV001, the efficacy period starts with the date and time of the first prophylactic dose following the completed PK sampling period (168 hours), and ends with the end of the treatment period as defined in Section 4.1.1.1. That is, if the initial PK sampling period is incomplete due to an aborted collection of blood samples following the PK injection (eg, because of a bleeding episode that required treatment), then the efficacy period will begin following a subsequent fully executed PK sampling period.

Adjustments Due to Surgical/Rehabilitation Periods

For analysis purposes, the efficacy period will be adjusted for all surgical/rehabilitation periods (major and minor). The start and end of the efficacy period are adjusted as follows:

- For all participants, the efficacy period continues up to 1 minute before the start of a surgical/rehabilitation period.
- For participants on a prophylactic regimen following the end of a surgical/rehabilitation period, the efficacy period for the prophylactic regimen re-starts at the first prophylactic dose following the end of the surgical/rehabilitation period.

Statistical Analysis Plan BIVV001-EFC16295 23-Aug-2021 Version number: 1

Bleeding episodes that occur during the surgical/rehabilitation period will be attributed to the surgical/rehabilitation period and hence not counted towards the ABR.

Adjustments Due to Large Injection Intervals

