4.4.1.4 Subgroup analyses

To assess the homogeneity of the treatment effect across various subgroups, analyses of the ABR will be performed across the following subgroups (categories with fewer than 5 participants may be combined with other categories):

- By bleeding phenotype at Baseline (estimated bleeds in prior 12 months, 0, >0-5, >5-10, >10)
- By number of target joints (none present, ≤ median of number present, > median of number present)
- By dosing and dosing interval compliance (<80%, $\ge80\%$)

The estimated mean ABR and the corresponding 95% CI will be provided, for each subgroup, using the same method as applied to the primary analysis. Forest plots will be provided.

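### The SAP's compliance rule fails doses and intervals that the protocol itself calls for: whole-vial round-up at >10 to <12 kg and >15 to <16 kg, and an authorised 5-day interval

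*SAP*

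**What the plan says.** **Scoring rule.** SAP 4.7.1.2 gives the per-injection rule: "An individual dose will be considered compliant if it is within 80%-125% of the study dose (50 IU/kg"). The dose is nominal. SAP 4.7.1 divides it by the participant's "most recent weight in kg prior to the dose of study drug". On the denominator, SAP 4.7.1.2 says "All prophylactic injections will be used to determine prophylactic dose compliance". A participant is dose compliant or interval compliant "if his respective rate is at least 80" per cent. An interval passes if it is within 36 hours of 7 days.

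**Dosing rule.** Protocol 6.1.6.2 says that, for prophylaxis and bleeds, the nominal "strength should be used for calculations and rounded up to the nearest whole vial". Baseline PK and Week 4 doses are the exception: they use actual potency and partial vials. Protocol 6.1.6.1 lists vials of 250, 500, 1000 and 2000 IU and allows actual potency of 80% to 125% of nominal. Inclusion criterion I 08 admits children from 10 kg. Protocol 6.1.2 lets the interval be shortened by 1 or 2 days in the <6 years cohort after consultation with the medical monitor.

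**Where the classes are used.** They feed the compliance tables and an ABR subgroup analysis in SAP 4.4.1.4: "By dosing and dosing interval compliance", cut at 80%. There, "categories with fewer than 5 participants may be combined with other categories".

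**The concern.** The scoring rule makes no allowance for vial rounding or for an authorised shorter interval. In a small child one 250 IU step is a large share of the dose, so rounding up can exceed the 125% ceiling.

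The rule can even reverse the meaning of compliance. At 11 kg, 500 IU (rounded down, against protocol 6.1.6.2) scores 91% and passes, while the rounded-up 750 IU scores 136% and fails. On an authorised 5-day schedule an on-time dose fails, while one that is 12 hours late (5.5 days) passes.

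In the dose factor, children dosed per protocol would be grouped with children who took wrong doses. In the interval factor, children on an authorised shorter interval would be grouped with children who missed or delayed doses. An ABR contrast between <80% and ≥80% would then not measure departure from the protocol. The interval problem can arise only under 6 years, so it can also produce an apparent difference between the age cohorts.

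**Working it through.** **Limits.** 0.80 × 50 = 40 IU/kg and 1.25 × 50 = 62.5 IU/kg. The SAP's own conversion of the interval tolerance is right: 36/24 = 1.5 days, so intervals of 5.5 to 8.5 days pass.

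**Dose, per injection.** For weight w (kg) and vial step s (IU), the rounded dose is D = s × ceil(50w/s), scored as 100 × D/(50w). I take s = 250 IU, the smallest whole-vial step and so the reading most favourable to the SAP.

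| Weight (kg) | Rounded dose (IU) | IU/kg | % of 50 IU/kg | Scored |
|---|---|---|---|---|
| 10 | 500 | 50.0 | 100 | pass |
| 10.1 | 750 | 74.3 | 149 | fail |
| 11 | 750 | 68.2 | 136 | fail |
| 11.9 | 750 | 63.0 | 126 | fail |
| 12 | 750 | 62.5 | 125 | pass |
| 15 | 750 | 50.0 | 100 | pass |
| 15.1 | 1000 | 66.2 | 132 | fail |
| 15.9 | 1000 | 62.9 | 126 | fail |
| 16 | 1000 | 62.5 | 125 | pass |
| 20.01 | 1250 | 62.5 | 124.9 | pass |

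A scan from 10 to 60 kg in 0.01 kg steps finds scores above 125% only at >10 to <12 kg and >15 to <16 kg. If a site rounded in 500 IU steps, the failing bands would be >10 to <16, >20 to <24 and >30 to <32 kg.

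**Week 4 dose.** 50 IU/kg by actual potency is 50/1.25 = 40 to 50/0.80 = 62.5 IU/kg nominal, so it always passes.

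**Dose, per child.** Assumptions: weekly doses at Weeks 0 to 52; weight updated at Day 1 and Weeks 4, 13, 26, 39 and 52; linear growth; vials recalculated at each visit weight. In the PK subgroup Day 1 is not scored, because "the efficacy period starts with the date and time of the first prophylactic dose following the completed PK sampling period" (SAP 4.1.1.2). That leaves 52 doses.

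- Start 11 kg, no growth: only Week 4 passes, 1/52 = 2%. Non-compliant.
- Start 11 kg, 2 kg/year: 12.0 kg at Week 26, so Weeks 26 to 52 (27 doses) and Week 4 pass, 28/52 = 54%. Non-compliant. With Day 1 scored (outside the PK subgroup), 28/53 = 53%.
- Start 11.9 kg, 2 kg/year: Weeks 1 to 3 fail, 49/52 = 94%. Compliant.
- Start 14.5 kg, 2 kg/year: Weeks 26 to 38 (13 doses) fail, 39/52 = 75%. Non-compliant. If the vial count stays at 750 IU, 100% pass.

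**Share of children.** The documents give no weight distribution. Assuming uniform start weights and growth of 0 / 2 / 3 kg/year, the share classed non-compliant while following the protocol is:

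| Start weights | Vials recalculated | Vial count fixed |
|---|---|---|
| 10-20 kg | 30 / 42 / 48% | 30 / 27 / 25% |
| 10-40 kg | 10 / 14 / 16% (about 7 / 9 / 10 of 65) | 10 / 9 / 8% |
| 12-40 kg | 4 / 8 / 11% (about 2 / 5 / 7 of 65) | 4 / 3 / 3% |

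**Interval.** |5 − 7| = 2 days > 1.5 days, so it fails by 12 hours. |6 − 7| = 1 day, so it passes.

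**The case against.** The SAP's arithmetic is sound: it openly defines compliance as closeness to 50 IU/kg, and the 125% ceiling absorbs round-up at all eligible weights outside two narrow bands. All analyses are descriptive, the Per Protocol Set does not use this metric, small categories may be combined, and every dose is listed by participant. This stands, and it limits the consequence. It does not remove the conflict, because SAP 4.7.1.2 presents the measure as compliance with the study protocol.

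The displayed formula for the dose rate is not legible in the text available to me. The denominator is inferred from the sentence that uses all prophylactic injections, so missed doses are taken not to enter the dose rate. The inference is well supported, but it is one.

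The Pharmacy Manual sets the vial count and is not among the documents. A scoring rule fixed at 250 IU would again fail a rounded dose at a site that rounds in larger steps. That stands as a point about the fix, which should name the vial rule in force. It does not weaken the finding, since larger steps widen the failing bands.

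The shares of children rest on assumed weights and growth, and the examples at 11 and 14.5 kg sit on thresholds: at 2 kg/year, 10.99 kg gives 29% and 14.51 kg gives 50%. The classification does not change, but the percentages are illustrations, not estimates. The interval point may affect no child, as it needs a 2-day reduction.

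**Conclusion.** The concern holds. Applied as written, the SAP scores as non-compliant every correctly rounded dose at >10 to <12 kg and >15 to <16 kg (with 250 IU steps), and every on-time interval under an authorised 2-day reduction. Children who follow the protocol can therefore be classed below 80%.

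How many cannot be derived from the documents. Under the assumed start weights that reach 40 kg, the dose problem alone gives about 2 to 10 of 65, so the <80% group may fall on either side of the 5-participant combining limit. If it is combined, the subgroup may not be plotted, but the compliance tables remain wrong. The number with a 2-day interval reduction cannot be estimated.

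The damage is confined to those tables and the ABR subgroup by compliance. The change should be made; it does not bear on the trial's main conclusions.

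**What to change.** Change the scoring in SAP 4.7.1.2 only. The passages need reconciling, and nothing here takes a view on which dose or interval is right.

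1. Keep the 80% to 125% band, and also count a whole-vial dose as compliant when it equals the dose given by the protocol's round-up rule at the most recent weight. State the vial step that the Pharmacy Manual sets. Check with 250 IU steps: at 15.1 kg, 750 IU (99%) passes by the band, 1000 IU (132%) passes as the rounded dose and 1250 IU (166%) fails; at 10.1 kg, 500 IU (99%) and 750 IU (149%) pass and 1000 IU (198%) fails.
2. Keep scoring doses given by actual potency and partial vials against 50 IU/kg. The PK-subgroup Day 1 dose lies outside the efficacy period and stays unscored.
3. Score each interval against the interval authorised for that child at that time, ±36 hours. If that is not available as data, flag these children and report their interval compliance separately.
4. In SAP 4.4.1.4, use the dose class and the interval class as two separate factors. The present bullet does not say whether they are pooled.

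**Cost.** SAP wording and one derivation of the rounded dose from weight. For item 3, the documents do not show that an authorised interval is recorded in the eCRF or ePD, so a data field or a sponsor log may be needed.
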